7.4. Blinding

As far as is possible, all measurements for the CRCT will be undertaken by staff who are blinded to the randomisation schedule. This will be achieved by using a member of the Clinical Research Network DeNDRoN team who are not involved with the study in any way, and who are located geographically in a different location from both the study team and the services. Where possible, the follow up visits will be

conducted in the same environment as the baseline visit (patient home or in a clinical environment). All visits for each participant will be done by the same person whenever possible/practicable.

7.5. Unblinding

There will be no need for unblinding for this study, as the clinical teams involved will already be unblinded.

7.6. Baseline Measurements & Data

The following assessments would be undertaken:

Patient:

- Mini-mental state examination (MMSE) [3]
- Montreal Cognitive Assessment (MoCA)[2]
- Geriatric Depression Scale (GDS-15)[5]
- Motor symptoms (Unified Parkinson's disease rating scale, Part III) [6]
- The dementia specific quality of life measure (DEMQOL) [8]
- Generic quality of life measure (EQ-5D-5L)
- Current management (e.g. medications prescribed, non-cognitive approaches used) would be recorded

Informant (regarding the patient):

- Neuropsychiatric symptoms (neuropsychiatric inventory (NPI)) [4]
- Cornell scale for depression in dementia[5]
- Activities of daily living (Bristol activities of daily living scale) [7]
- Dementia Cognitive Fluctuation Scale (DCFS-R)
- The dementia specific quality of life measure (DEMQOL proxy) [8]
- Generic quality of life measure (Proxy EQ-5D-5L)
- Baseline Global rating scale (regarding patient)
- Global rating scale(regarding patient)

- Use of health care and personal social services and patient and care incurred costs collected via questionnaires based on a bespoke questionnaire derived from the Client Service Receipt Inventory (CSRI) and the Resource Utilisation in Dementia (RUD) instrument.

Informant (regarding carer own health and wellbeing):

- Hospital Anxiety and Depression Scale (HADS) [9]
- Generic quality of life measure (EQ-5D-5L)
- Zarit burden scale[10]
- Use of Health and Personal social services (collected on same Questionnaires reported above)

Researcher to complete about the patient :

- Galvin Lewy Body Composite Score
- Global outcome scale

Clinician:

- Clinician Toolkit Use Score (administered either on paper or electronically)

7.7. Trial Assessments

Measurements will be conducted at 3 months (+2 weeks) and 6 months (+2 weeks) after the baseline visit as listed in table 1. The primary outcome for the study will be the 6 month assessment. If it is determined at the follow up visits that the patient is no longer able to complete the additional measurements, the visit may continue with the informant/carer providing information as a participant. The informant/carer does not need to be present at all follow up visits as some questions can be completed on the telephone.

[figure not shown]
Table 1.

	Baseline	3 Months	6 Months
Patient			
Consent	X		
MMSE	X	X	X
MoCA	X	X	X
GDS-15	X	X	X
UPDRS-III	X	X	X
DEMQOL	X	X	X

EQ-5D-5L	X	X	X
Carer/informant relating to patient			
Consent	X		
NPI	X	X	X
Cornell	X	X	X
BADL	X	X	X
DCFS-R	X	X	X
DEMqoL-Proxy	X	X	X
Proxy EQ-5D-5L	X	X	X
Baseline Global outcome scale (regarding patient)	X		
Global outcome (regarding patient)		X	X
Use of services and costs*	X	X	X
Time and travel questionnaire*			X
Carer/informant relating to themselves			
Zarit	X	X	X
EQ-5D-5L	X	X	X
HADS	X	X	X
Use of services and costs*	X	X	X
Time and travel questionnaire*			X
Researcher relating to patient			
Galvin Lewy Body Composite Score	X		X
Global Outcome Scale		X	X

*The same questionnaires will give the information of the services used, and time and travel needed for both the patient and the carer

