3. AIMS, OBJECTIVES AND OUTCOME MEASURES

3.1. Aims and Objectives

The overall aim of the programme is firstly to improve the recognition and prompt diagnosis of LBD in routine NHS secondary services using a simple clinical tool for assessment of key symptoms. Secondly, for clinicians to improve patient management after diagnosis using an evidence based management toolkit.

Work package 5 will conduct a pilot cluster randomised controlled trial (cRCT) to test the management toolkit. It will look to:

- Determine feasibility of use of the intervention
- Assess the impact of the management toolkit on patient management, health outcomes and impact on carers/informants
- Provide an exploratory comparison of the cost-effectiveness of the new assessment and management toolkit for LBD with usual care

The cRCT will provide data on impact on patient symptoms, outcomes, quality of life and informant/carer stress (quality of life). It will provide data on rates of consent and drop out, as well as suitability of the outcome measures. It will also provide data on the use of the management toolkit by clinicians.

An exploratory health economic analysis will be conducted using data collected from WP1 and WP5 to estimate the overall cost effectiveness of implementing the new management toolkit in the NHS compared to usual care, as well as economic impact on the NHS, personal social services, informal carers and relatives.

Hypothesis:

We hypothesise that DLB and for PDD subjects treated in services randomised to implementing the management toolkit will result in symptom improvement, increased quality of life and decreased carer stress at 6 months compared to baseline.

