3.2. Outcome Measures

Outcome measures:

- Symptom measurement (reduced Neuropsychiatric Inventory (NPI) score; lower unified Parkinson's disease rating scale score; lower Cornell depression score, Geriatric Depression Scale)
- Patient quality of life (patient EQ-5D-5L and carer proxy EQ-5D-5L for incapacitated patients; patient DEMQOL and carer DEMQOL-proxy scales)
- Carer stress and quality of life (carer EQ-5D-5L; HADS; and Zarit burden scale)
- Time spent caring for the person with dementia
- Changes in management (including changes in prescribed medication)
- Rates of cognitive decline (MMSE; and MoCA)
- Global outcomes (observer and carer rated)
- Health economic measures:
 - Primary and secondary health care resource use, use of personal social services
 - Cost to primary and secondary health care and personal social services
 - Patient costs (time and travel costs of accessing health care services)
 - Unpaid costs to carers based on the time spent caring for the person with dementia
 - Patient quality adjusted life years (QALYs) estimated from patient responses to the EQ-5D-5L and DEMQOL, and carer responses to proxy EQ-5D-5L and the DEMQOL-proxy measures, respectively
 - Carer QALYs estimated from carer responses to a carer's EQ-5D-5L

- Incremental cost per QALY gained calculated from the total costs and QALYs of the patient and the carer in order to compare the new assessment and management toolkit with usual care

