- The delegated staff member will discuss the study with the patient (or consultee) and answer any questions. Staff will be blinded to the randomisation schedule wherever possible.
- Informed consent will be sought from the patient in the first instance. The study team member will perform an assessment of mental capacity to ensure the patient is able to consent to the study. If not, and the patient appears willing, an opinion will be sought from the consultee.
- Informed consent will also be sought from the informant/carer as a participant in the study.
- Baseline measurements will be performed (patient and informant/carer).

- Health economic data will be collected using patient and carer responses to the EQ-5D and DEMQOL questionnaires as well as the use of health and social services questionnaire and the time and travel questionnaire.

Follow up visits – approximately 3 months (+/- 2 weeks) and 6 months (+/- 2 weeks) after baseline

- Wherever possible the follow up visits will be performed in the same environment as the baseline visit, and by the same delegated study team member.
- Measurements will be performed at 2 further study visits, approximately 3 months and 6 months after baseline.
- If the patient is no longer able to complete the measures, the visit will continue with the informant providing carer information as a participant.
- If the informant/carers is not able to attend all follow up visits, some information may be collected by telephone.
- Health economic data collection will be repeated. In addition a time and travel questionnaire will be administered at 6 months to estimate the time and travel costs of accessing health and personal social services.
- If it is felt not appropriate to do the time and travel questionnaire at the last visit, it can be left with participant for completion and returned by post.

Data Collection

Data will be collected and used for the study from:

- Study visits: data collected from the measurements used at the baseline, 3 month and 6 month visits, as well as health economic data.
- Clinician questionnaire: data collected from the clinician toolkit use questionnaire completed approximately 6 months following service randomisation and at the end of the study.

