8.2. Assessment of Compliance

Clinicians from participating services in the intervention arm will be asked to complete a questionnaire regarding use of the management toolkit. This will indicate:

- The level of completion and reasons
- Rates of compliance
- User experience

Consent will be implied through completion of the questionnaire. All clinicians in the intervention arm will be given the opportunity to complete the questionnaire at approximately 6 months following service randomisation and at the end of the study. This data will be used to answer key questions about the feasibility of use of the management toolkit in standard clinical care.

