				
The questionnaires relating to the researcher have been added to the schedule of events.
 
The global outcome scale (carer version) has been renamed ‘Baseline Global outcome scale (regarding patient)’.
 
The global outcome scale (patient version) has been removed from the list of patient questionnaires, renamed ‘global outcome scale (regarding patient)’ and added to the informant/carers list of questionnaires.
 
The procedure for those patients who lose capacity during the study has been updated. The research team would seek a consultee rather than remove the patient from the study should they lose capacity during the study. This has also been amended on the IRAS Form (A35).
 
The clinician toolkit use questionnaire may be sent in either paper or electronic format to the clinician and so this has been stated in the protocol.
 
Amendments to Questionnaires:
 
The 2 health economics questionnaires have been amended as per description below.
 
Time and Travel Questionnaire - Further instruction as to how to calculate the distance travelled has been added to Questions A6, A7, C6 & C7
 
Use of Healthcare and Social Services- The wording has been altered in questions A1, A2, A3 & C1. A box has been added to table in Questions B1, B2, B3 & B4 to indicate whether the service stated was NOT used. Question C4 has been added to give the participant the option to opt out of answering questions relating to their income.

--	--	--	--	---

				
Question D1 referring to the patients medication profile has been removed from the new version of the questionnaire. Questions I to K have been removed from this questionnaire.
 
Other: An information document for practitioners has been produced by the trial team.
 
Two Trusts have been added to the list of research sites in the IRAS form as listed below: City of Sunderland Hospitals NHS Foundation Trust Ipswich Hospitals NHS Foundation Trust.

2.0 (minor amendment)	3.0	30.06.16	[name]	
Minor amendment made to the coding in ‘Time and Travel’ and ‘Use of Health and Personal Social Services’ questionnaires. Instead of yes = 1 and no = 2 as written in the old version, the new version states now yes = 1 and no = 0. Don’t know was changed to be recorded as 555 rather than the next sequential number.

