3.0 (minor amendment)	4.0	19.10.2016	[name]	
Amendments to the protocol:
 
[name] has replaced [name] as Project Manager. Her details have been added to the Key Contacts on page 4.
 
The frequency of the Clinician Toolkit Feedback Questionnaire has been amended on pages 26 & 28. The Clinicians randomised to receive the management toolkit will now be asked to complete the questionnaire at two time points (approximately 6 months post randomisation and at study end).
 
Amendments to the Clinician Toolkit Questionnaire: The Questionnaire has been updated to reflect the changes in frequency that it will be completed and to make it more general about the clinicians’ view of the toolkit, so incorporating all patients who have been managed rather than per patient.

10.0 (minor amendment)	5.0	07.06.2018	[name]	Amendments to the protocol: [name] has replaced [name] as Trial Statistician. His details have been added to the Signature page on pg. 3 and the key trial contacts on pg. 6.

{Enter all amendments to the protocol here whether substantial or non-substantial. Substantial amendments will require approval by the NHS REC. Non-substantial amendments should be sent to the NHS REC for acknowledgement only}

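### Changes in management is a listed outcome, but the protocol schedules no record of management or medication at 3 or 6 months

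*Protocol*

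**What the plan says.** Section 3.1 of the protocol gives as one objective of the pilot: "Assess the impact of the management toolkit on patient management, health outcomes and impact on carers/informants". Section 3.2 lists as an outcome "Changes in management (including changes in prescribed medication".

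Section 7.6, the list of baseline assessments, includes the item "Current management (e.g. medications prescribed, non-cognitive approaches used) would be recorded". For follow-up, section 7.7 has no list of its own and points to the table: "Measurements will be conducted at 3 months (+2 weeks) and 6 months (+2 weeks) after the baseline visit as listed in table 1". The same section makes the 6-month assessment the primary one.

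Section 7.7.1 names the study's data sources. From study visits they are "data collected from the measurements used at the baseline, 3 month and 6 month visits, as well as health economic data". The other source is the clinician questionnaire on toolkit use.

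On the service-use questionnaire, which is given at all three visits, the amendment history in section 14.1 records: "Question D1 referring to the patients medication profile has been removed from the new version of the questionnaire".

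**The concern.** A change needs a measurement at both ends. The protocol provides one end, in the baseline list, and schedules nothing at the other.

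This outcome is closer to the intervention than the rest. The toolkit is a guidance document for clinicians (section 8.1), so what it can alter first is how they manage the patient. Effects on symptoms, quality of life and carer burden would come through that. If the 6-month scores differ little between arms, the pilot would want to know whether management differed at all. Without follow-up data on management, a toolkit that changed nothing in practice cannot be told apart from one that changed practice without moving the scores. That distinction matters for deciding on a definitive trial.

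An analysis plan cannot repair this. It can define how change is scored, but it cannot supply data that no visit collects.

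**Working it through.** No formula applies. The check sets the outcome against each place where follow-up data could come from.

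1. **Table 1.** It has 7 patient rows, 11 carer rows about the patient, 5 carer rows about themselves and 2 researcher rows: 7 + 11 + 5 + 2 = 25. None is current management, medication or treatment approach.

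2. **Comparison with other outcomes in section 3.2.** The NPI, UPDRS, Cornell, GDS, EQ-5D-5L, DEMQOL, HADS, Zarit, MMSE, MoCA and global outcomes each have a row marked at 3 and 6 months. Changes in management does not.

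3. **Count of scheduled records of management.**

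| Source | Baseline | 3 months | 6 months |
|---|---|---|---|
| Section 7.6 text | yes | – | – |
| Table 1 | no | no | no |

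The text gives 1 of 3 visits and the table 0 of 3. Both give 0 of the 2 follow-up visits.

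4. **Section 7.7.1 data sources.** Visit measurements lead back to Table 1. A review of notes for follow-up management is not mentioned. Section 7.1.1 mentions medical records only for finding eligible patients.

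5. **Service-use questionnaire.** It is given at baseline, 3 and 6 months and may partly reflect non-drug management, such as contacts with services. The outcome expressly includes prescribed medication, and the one medication item known to have been in that questionnaire was removed. The amendment history is used here only as evidence of what the current questionnaire contains.

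6. **Clinician questionnaire.** Section 8.2 restricts it to one arm: "Clinicians from participating services in the intervention arm will be asked to complete a questionnaire regarding use of the management toolkit". The amendment history says it now asks for a general view, "incorporating all patients who have been managed rather than per patient". It therefore cannot provide a patient's management at 6 months, and it has no control arm to compare with.

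7. **Reach.** The gap is in the schedule, so it applies to every planned patient: 60 + 60 = 120.

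8. **The baseline record.** Section 7.1.1 accepts that the baseline visit may come after the toolkit has been used. In the intervention arm, management recorded at baseline may already reflect the toolkit. A change from baseline, or a comparison adjusted for baseline management, could then remove part of the effect being sought. The single scheduled measurement is thus a weak anchor, which makes the 6-month record more important.

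**The case against.** The strongest reply is that Table 1 is not exhaustive. It omits current management even at baseline, where section 7.6 says it is recorded, so absence from the table does not prove that nothing is collected. Data go onto paper case report forms that are not shown, and these may carry a medication page at every visit. The medication question may have been removed precisely because such a page made it redundant. This stands as far as it goes: a reader might infer that the outcome is impossible to compute, and the documents do not establish that. They do show that the protocol schedules no follow-up collection. Baseline has its own list in the text, whereas follow-up has only the table, so a site working from the protocol would have no instruction to record management at 3 or 6 months.

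Two further inferences are tempting and not supported:

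- **Follow-up drug costs are missing from the economic evaluation.** This would rest on one removed question in a questionnaire that is not shown. Section 10 says resource data come from the case report forms, whose content is unknown.
- **Feasibility and compliance cannot be assessed because toolkit use is not logged per patient.** No listed outcome requires per-patient use. Section 3.1 promises data on use by clinicians, section 8.2 takes compliance from the clinician questionnaire, and the move away from per-patient reporting was deliberate. Feasibility can be summarised at clinician level, with a second questionnaire at study end.

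It is also fair to say that this is an exploratory pilot with many outcomes and no single primary measure. That limits the weight of the point.

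**Conclusion.** The point holds as a mismatch between outcome and schedule. Impact on management is an objective and change in management is a listed outcome, yet the protocol schedules its measurement at 0 of 2 follow-up visits. Followed as written, the outcome cannot be derived from the scheduled data for any of the 120 planned patients.

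This rests on two assumptions: that sites collect what the protocol tells them to, and that the case report form adds nothing beyond it. If the form does record medication and other treatment at follow-up, what remains is a documentation gap in section 7.7 and Table 1. Service-use data soften the gap for non-drug management but not for prescribing.

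The importance is moderate. It affects one of several exploratory outcomes and does not threaten the pilot as a whole, but that outcome is the most direct reading of whether the toolkit did anything.

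**What to change.** Add a row to Table 1 for current management (medications prescribed and non-drug approaches), marked at baseline, 3 and 6 months in both arms. Alternatively, name medical records in section 7.7.1 as the source at those three times. If the case report form already captures this, the row only documents existing practice.

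Compare the arms on management at 6 months. Baseline management can be reported and used in a supporting analysis, but the comparison should not rely solely on adjusting for it, because baseline may follow first use of the toolkit.

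The cost is a short case report form item at visits that already take place, or a brief look at the notes, plus a protocol amendment whose classification section 12.9 leaves to the sponsor. No extra visits or participants are needed.

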7.7.1. Flow Chart

Explanatory notes for flow chart:

Management Toolkit:

- Participating services will be cluster randomised to either the intervention arm (management toolkit) or the control arm (usual management care).
- Services that are randomised to the intervention arm will receive the management toolkit for use in their contacts with patients who require management, as well as appropriate training to use the toolkit.

- The management toolkit will be used according to clinician judgement and is a recommended guideline. It may be used at a single clinic visit, or over multiple visits/patient contacts. The clinicians may use the sections of the toolkit that they feel are appropriate for the patient.
- Clinicians in the intervention arm will be asked to complete a questionnaire regarding their use of the toolkit at 6 months after randomisation.

Screening and Recruitment:

- Potential participants will be identified by network staff, the clinical team or the study team through the review of medical records and patient lists at participating services.
- If appropriate, a study invite letter and participant information sheet may be given at the clinical appointment where there is a need for management identified e.g. an appointment for diagnosis.
- Otherwise, eligible patients will be discussed with a clinician after the clinical appointment regarding the need for a consultee to be present at the study visit. Contact details will be obtained if agreed it is appropriate to continue and the invite letter and relevant participant information sheet(s) will be posted.
- In all cases, a minimum of 24 hours will be given to consider the information, and longer if they need time to discuss with family/friends.
- All potential participants will have the option to contact the team straight away if they definitely do not want to take part in the study.
- If no 'opt out' is received, a follow up telephone call will be made by a member of the study team to answer questions and arrange the baseline study visit in the presence of an informant/carer.
- The baseline visit will be additional to routine care and will be made as soon as is reasonably and practically possible after the patient has been identified for the study. The visit may take place in a clinical environment or at the patient's home.
- An eligibility screening log will be completed.

Baseline Visit:

- The delegated staff member will discuss the study with the patient (or consultee) and answer any questions. Staff will be blinded to the randomisation schedule wherever possible.
- Informed consent will be sought from the patient in the first instance. The study team member will perform an assessment of mental capacity to ensure the patient is able to consent to the study. If not, and the patient appears willing, an opinion will be sought from the consultee.
- Informed consent will also be sought from the informant/carer as a participant in the study.
- Baseline measurements will be performed (patient and informant/carer).

- Health economic data will be collected using patient and carer responses to the EQ-5D and DEMQOL questionnaires as well as the use of health and social services questionnaire and the time and travel questionnaire.

Follow up visits – approximately 3 months (+/- 2 weeks) and 6 months (+/- 2 weeks) after baseline

- Wherever possible the follow up visits will be performed in the same environment as the baseline visit, and by the same delegated study team member.
- Measurements will be performed at 2 further study visits, approximately 3 months and 6 months after baseline.
- If the patient is no longer able to complete the measures, the visit will continue with the informant providing carer information as a participant.
- If the informant/carers is not able to attend all follow up visits, some information may be collected by telephone.
- Health economic data collection will be repeated. In addition a time and travel questionnaire will be administered at 6 months to estimate the time and travel costs of accessing health and personal social services.
- If it is felt not appropriate to do the time and travel questionnaire at the last visit, it can be left with participant for completion and returned by post.

Data Collection

Data will be collected and used for the study from:

- Study visits: data collected from the measurements used at the baseline, 3 month and 6 month visits, as well as health economic data.
- Clinician questionnaire: data collected from the clinician toolkit use questionnaire completed approximately 6 months following service randomisation and at the end of the study.

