2.2 The need to improve the recognition and management of PDD

Patients with PD are often reviewed regularly in neurology or geriatric medicine services, but there are still problems in recognising and diagnosing PDD. Only around 1 in 3 of those with PDD are currently recognised and diagnosed, and this often occurs late in the disease.

Some of the key reasons for the difficulties in recognising, diagnosing and appropriately managing patients with PDD include:

- 1) Cognitive impairment develops insidiously and at a variable time after PD diagnosis.
- 2) Initial symptoms such as fluctuation, attentional problems and visual hallucinations may be thought to be related to medication side effects.

2.3 The need to improve the recognition and management of LBD (DLB and PDD)

When dementia is recognised there are effective pharmacological and non-pharmacological strategies for cognitive symptoms, psychosis, sleep disturbance and other psychiatric problems. The recognition of dementia allows the provision of support, education and advice, access to services, financial and other benefits and opportunities for future planning and attending to medico-legal issues. This improves long term outcome in terms of reducing carer stress and delaying the need for care.

There is a clear need to improve the assessment, diagnosis and management of LBD both in memory/dementia services and movement disorder services. There is currently no single, simple tool which incorporates the range of clinical symptoms for LBD, and there is no unified evidence based management care pathway. This study is looking to develop a management toolkit for routine use in patients with DLB and PDD in NHS services.

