9.2. Statistical Analyses

Hypothesis

For the definitive trial we hypothesise that DLB and for PDD subjects treated in services randomised to implementing the management toolkit will result in symptom improvement (reduced neuropsychiatric inventory score, lower unified Parkinson's disease rating scale score, greater improvement in CGIC global and symptom ratings), increased quality of life (DEMQOL and DEMQOL-proxy scales) and decreased carer stress (HADS, Zarit burden scale) at 6 months compared to baseline. In this pilot study, we will conduct an exploratory analysis where we will rehearse the analysis proposal for the full trial.

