9.2.2. Statistical Analyses

As the management tool covers both DLB and PDD it will be appropriate to undertake exploratory analysis on the combined PDD and DLB subject group. As the hypothesis concerns changes in symptom scores between baseline and 6 months we will use T-tests in an exploratory analysis to compare the means of two samples when data is normally distributed and a Wilcoxon Signed test will be used to compare the medians of two samples when data is skewed. The association of a binary outcome with a categorical predictor with 2 or more levels will be tested using the Chi-square test. Further analysis involving the data measured at baseline, 3 months and 6 months will be done by using a linear mixed regression model to test for between group and between time differences.

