9.3. Statistical Size Calculations

This is a pilot study and the sample sizes may be insufficient to test the hypothesis. However information on the variability of continuous variables measuring the symptoms such as neuropsychiatric inventory score will be used in power calculations for a larger study. The choice of 30 cases in each arm of the pilot study is a rule of thumb advocated by clinical trial researchers (ref Lancaster G.A 2002).

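### Follow-up UPDRS-III visits are matched to baseline, where possible, on setting and rater but not on time of day or time since the last dopaminergic dose, adding avoidable noise to motor change

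*Protocol*

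**What the plan says.** Section 7.6 of the protocol lists "Motor symptoms (Unified Parkinson's disease rating scale, Part III") among the patient assessments, and Table 1 in section 7.7 schedules it at all three visits. The hypothesis in section 9.2 includes a "lower unified Parkinson's disease rating scale score". Section 9.2.2 makes change the quantity of interest: "As the hypothesis concerns changes in symptom scores between baseline and 6 months we will use T-tests".

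On visit conditions, section 7.7.1 asks that "the follow up visits will be performed in the same environment as the baseline visit, and by the same delegated study team member". The sentence opens with a wherever-possible qualifier, and section 7.4 qualifies both the setting and the rater in the same way. The follow-up window is given in weeks. The only medication item in section 7.6 is current management, with prescribed drugs as an example. Time of day, time of the last dose and motor state at examination do not appear.

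Section 9.3 says that "information on the variability of continuous variables measuring the symptoms" will be used in power calculations for a larger study. Its named example is the NPI.

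**The concern.** The protocol already accepts that rating conditions should be kept alike within a patient, and it names two of them. For a motor examination in treated Parkinson's disease, where the patient stands in the dosing interval is a third. That premise is general clinical knowledge; the protocol does not state it. As written, a patient could be examined soon after a dose at baseline and late in the interval at 6 months, and the difference would be recorded as motor change.

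Two uses of the data are affected. The first is the exploratory comparison of UPDRS-III change. The second is what the pilot hands on: section 3.1 promises data on the suitability of the outcome measures, and section 9.3 promises information on variability. If UPDRS-III change proves noisy and the times were not captured, nobody can tell an unsuitable scale from one rated at mismatched times. An analysis plan cannot repair this, because it cannot recover a time that was not recorded.

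**Working it through.** **Inputs from the protocol**
- Patients: 60 in WP5A and 60 in WP5B (Trial Summary), so 120. WP5B requires a Parkinson's disease diagnosis (section 6.1), so 60/120 = one half.
- The 30 per arm is a rule of thumb (section 9.3). No alpha, power, effect size or SD lies behind it, so it cannot be re-derived. The totals agree: 30 × 2 arms × 2 work packages = 120, and 240 with carers.
- No UPDRS-III SD is given, nor the number of patients on dopaminergic drugs.

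**Assumptions (not in the protocol)**
- SD of 6-month change free of timing effects: 8 points.
- Per-visit SD due to timing, t: 3, 5 or 7 points, independent between visits.

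**Formula.** A change score uses two visits, so Var(change) = 8² + 2t².

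| t | Var(change) | SD | Ratio to 64 |
|---|---|---|---|
| 3 | 64 + 18 = 82 | 9.06 | 1.28 |
| 5 | 64 + 50 = 114 | 10.68 | 1.78 |
| 7 | 64 + 98 = 162 | 12.73 | 2.53 |

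For fixed precision the number of patients scales with the variance, so the last column is also the factor on sample size.

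**Why these are ceilings.** The table applies the timing noise to every patient and treats all of it as removable. Sections 9.2.1 and 9.2.2 analyse DLB and PDD together. If only half the combined group were affected, the average variance would be 64 + t²:
- t = 3: 73, ratio 1.14
- t = 5: 89, ratio 1.39
- t = 7: 113, ratio 1.77

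Matching that removed only half the timing variance would save correspondingly less.

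**Effect on a later trial.** Take a true difference of 0.5 timing-free SDs, two-sided alpha 0.05, 80% power and no allowance for clustering. Let s be the timing SD per visit as a fraction of the timing-free change SD, so that the variance factor is 1 + 2s².

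| s | SD multiplier | n per arm |
|---|---|---|
| 0 | 1.00 | 63 |
| 0.2 | 1.04 | 68 |
| 0.3 | 1.09 | 75 |
| 0.5 | 1.22 | 95 |
| 0.7 | 1.41 | 125 |

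These figures show direction and scale under stated assumptions. They do not estimate this trial's SD.

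**The case against.** The protocol says nothing false here; it is silent. Data go onto paper CRFs (section 11.1) that are not shown, and an examination or dose time could be recorded there. That stands, and it limits the claim to what the protocol lists. Setting and rater are themselves only preferences, so the protocol does not aim at strict standardisation; the fix should carry the same qualifier. UPDRS-III is one of many exploratory outcomes, section 9.3 concedes that the sample may be too small to test the hypothesis, and UPDRS-III enters the power-calculation sentence only by extension from the NPI. If the definitive trial kept the same pragmatic visits, the SD observed under them would be the right planning input. All of this keeps the severity low. It does not remove the cheap gain in precision.

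A reader might infer three stronger things.

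- **That the toolkit effect is confounded with dose timing.** The documents do not show this. Timing that varies alike in both arms is noise. Uneven scheduling across about 8 services, or changes of regimen under the toolkit, could make it unequal between arms, but nothing in the protocol indicates that they do.
- **That MMSE and MoCA share the problem.** Section 2.2 on PDD says "Initial symptoms such as fluctuation, attentional problems and visual hallucinations may be thought to be related to medication side effects". That explains why diagnoses are missed; it does not describe time-of-day swings in test scores. Cognitive fluctuation is measured separately by the DCFS-R at every visit.
- **That UPDRS-III should be analysed only in visits matched on timing.** Matching at follow-up is a post-randomisation feature. Change in prescribed medication is itself an outcome (section 3.2), so the toolkit may affect which visits match. Such a restriction could bring bias into a comparison that otherwise has mainly noise.

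**Conclusion.** The point holds as a minor one about precision. Sections 7.4 and 7.7.1 match visits on setting and rater where possible, leave out time of day and time since the last dopaminergic dose, and the listed data would not allow either to be examined later. The consequence is avoidable noise in the 6-month UPDRS-III change and in any motor SD passed on.

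Its size is not in the documents. Under an assumed change SD of 8 and timing SDs of 3 to 7 points, the variance factor is at most 1.28 to 2.53. It is smaller to the extent that patients are untreated, that timing is already similar between visits, or that matching is partial. The point weighs most in WP5B and may be weaker in WP5A, where the protocol does not say how many patients take dopaminergic drugs.

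**What to change.** - **Sections 7.4 and 7.7.1:** add that, wherever possible, each participant's visits are booked at a similar time of day and, for those on dopaminergic medication, at a similar time since their last usual dose. State that no patient's medication is changed or withheld for this.
- **CRF:** at each visit record the time of the last dose and the time of the UPDRS-III examination. If matching proves impractical, recording these times is the minimum.
- **Reporting:** describe the spread of these times by arm alongside the UPDRS-III SD. The definitive trial's planners can then judge how far the SD reflects timing, and any imbalance between arms becomes visible.

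The cost is protocol wording, two CRF fields and slightly less freedom when booking visits that already have to suit a rater, a setting and an informant. No visit or procedure is added.
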